Dose finding cohorts: Cohort A: will identify the MTD/RP2D ₁ of the xentuzumab/abemaciclib combination in patients with solid tumours. Cohorts B, C & D (dose finding): will identify the MTD/RP2D ₂₋₄ of the xentuzumab/ abemaciclib combination on a background therapy of letrozole OR anastrozole OR fulvestrant (referred to as “triplets”) in postmenopausal women with locally advanced/metastatic hormone receptor positive (HR+) breast cancer. Expansion cohorts: Cohort E: will further characterize safety, tolerability, PK, and preliminary efficacy of the xentuzumab/abemaciclib combination in a single-arm dose expansion group of non-small cell lung cancer patients. Cohort F: will investigate the efficacy and PK of the triplet combination xentuzumab/abemaciclib and fulvestrant in a single-arm expansion group of patients with locally advanced/metastatic hormone receptor positive (HR+) breast cancer and only non-visceral disease who have progressed following endocrine therapy (aromatase inhibitor) and prior CDK inhibitor treatment. Cohorts D1 and D2: will explore anti-tumor activity of the triplet combination xentuzumab, abemaciclib and fulvestrant in patients with locally advanced/metastatic HR+ breast cancer visceral disease (Cohort D1) or non-visceral disease (Cohort D2) who have progressed following endocrine therapy (aromatase inhibitor or Selective Estrogen Receptor Modulator). No. of patients: N= approximately 148 Dose finding cohorts: Cohort A: approx. 12 evaluable patients Cohort B: approx. 12 evaluable patients			

Name of company:	Boehringer Ingelheim	
Name of finished product:	Not applicable	
Name of active ingredient:	Xentuzumab (BI 836845)	
Protocol date: 30 Nov 2016	Trial number: 1280.18	Revision date: 04 Mar 2022
	
Cohort C: approx. 12 evaluable patients Cohort D (dose finding): approx. 12 evaluable patients Expansion cohorts : Cohort E: 20 evaluable patients Cohort F: 20 evaluable patients with non-visceral disease Cohort D1: 30 evaluable patients with visceral disease Cohort D2: 30 evaluable patients with non-visceral disease
	
total entered:	Approximately 148 evaluable patients	

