2.2 TRIAL OBJECTIVES

For each dose finding cohorts (A, B, C and D):

The primary objective of each dose finding cohort is to determine the maximum tolerated dose (MTD) / recommended phase II dose (RP2D) of xentuzumab in combination with abemaciclib with or without hormonal therapy (letrozole, anastrozole, fulvestrant). Dose limiting toxicities (DLT) will be assessed during the first treatment cycle to assess the MTD/RP2D.

In case that no MTD is reached a RP2D dose will be determined taking into account safety data and other available information. This will be agreed with the Steering Committee.

[figure not shown]
For each expansion cohorts (E, F, D1 and D2):

The objective of the cohort E is to assess the anti-tumour activity of xentuzumab in combination with abemaciclib in patients with non-small cell lung cancer.

Cohort F will assess the anti-tumour activity of the triplet combination xentuzumab / abemaciclib and fulvestrant in a single-arm expansion group of patients with locally advanced / metastatic hormone receptor positive (HR+) HER2- breast cancer who have progressed following prior therapy with an aromatase inhibitor and a different CDK4/6 inhibitor (excluding abemaciclib).

The primary objective of cohorts D1 and D2 is to assess the anti-tumour activity of the triplet combination xentuzumab, abemaciclib and fulvestrant in patients with locally advanced / metastatic HR+ breast cancer who have progressed on prior endocrine therapy. Cohort D1

will assess the anti-tumour activity for subjects with visceral metastasis and Cohort D2 for subjects with non-visceral metastasis.

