 - b. Relapsed with radiologic evidence of progression within 1 year from completion of adjuvant endocrine therapy, with no subsequent endocrine therapy received following progression.
 - c. Relapsed with radiologic evidence of progression more than 1 year from completion of adjuvant endocrine therapy and then subsequently relapsed with radiologic evidence of progression after receiving treatment with either an antiestrogen or an aromatase inhibitor as first-line endocrine therapy for metastatic disease. Patients may not have received more than 1 line of endocrine therapy or any prior chemotherapy for metastatic disease.
 - d. Presented de novo with metastatic disease and then relapsed with radiologic evidence of progression after receiving treatment with either an antiestrogen or an aromatase inhibitor as first-line endocrine therapy for metastatic disease. Patients may not have received more than 1 line of endocrine therapy or any prior chemotherapy for metastatic disease.
12. For cohort D1 (visceral disease) patient must have at least one documented visceral metastasis; for cohort D2 (non-visceral disease), patient must not have any visceral metastasis.

Cohort F only:

13. Patients with resistance to prior therapy with an aromatase inhibitor (AI) and CDK4/6 inhibitor (excluding abemaciclib) for locally advanced or metastatic breast cancer, defined as radiologic evidence of disease progression while on, or within 30 days after last dose of AI and/or CDK4/6 inhibitor (excl. abemaciclib) administered as first-line therapy for locally advanced or metastatic disease. Patients may not have received more than 1 line of prior endocrine based therapy or any prior chemotherapy for advanced/metastatic disease.
14. Patient must not have any visceral metastasis (example of allowed lesions are in breast, lymph nodes, soft tissue, bone).

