7. Prior anti-cancer chemotherapy, biological or radiation therapy, androgens, thalidomide, other anticancer agents, or any investigational drug within 21 days (14 days for non-myelosuppressive agents); and/or 4 weeks for immunotherapy, before starting any of the trial drugs. For cohort F only: prior palbociclib or ribociclib treatment within 14 days before starting any of the trial drugs.
8. Have received prior treatment with chemotherapy (except for neoadjuvant/adjuvant chemotherapy), fulvestrant, everolimus, alpelisib or abemaciclib. For cohorts D1 and D2 only: prior treatment with palbociclib or ribociclib is also excluded
9. Prior radiotherapy to $\geq 25\%$ of bone marrow regardless of when it was received
10. Unresolved treatment related toxicity from previous therapy of > CTCAE grade 1 at study entry (except for stable sensory neuropathy \leq CTCAE grade 2 and alopecia)
11. Previous treatment with IGF-1R targeting compounds
12. Have clinical evidence or history of central nervous system metastasis. Screening is not required for enrolment.

Proprietary confidential information © 2024 Boehringer Ingelheim International GmbH or one or more of its affiliated companies

13. The patient has serious and/or uncontrolled pre-existing medical condition(s) that, in the judgement of the Investigator, would preclude participation in this study, including interstitial lung disease, severe dyspnoea at rest or requiring oxygen therapy.
14. Inadequate bone marrow reserve or organ function as demonstrated by any of the following: ANC $< 1.5 \times 10^9/L$, platelets $< 100 \times 10^9/L$, haemoglobin $< 90g/L$, ALT $> 2.5 \times ULN$ or $> 5 \times ULN$ in the presence of liver metastases, total bilirubin $> 1.5 \times ULN$ or $> 3 \times ULN$ in patients with Gilbert's Syndrome, serum creatinine $> 1.5 \times ULN$ concurrent with creatinine clearance $\leq 50 \text{ mL/min}$.
15. Pre-existing renal disease including glomerulonephritis, nephritic syndrome, Fanconi Syndrome or renal tubular acidosis
16. Refractory nausea and vomiting, chronic GI diseases, inability to swallow the product, or previous significant bowel resection that would preclude adequate absorption of abemaciclib or resulting in baseline Grade 2 or higher diarrhoea.
17. History of hypersensitivity to active or inactive excipients of xentuzumab, abemaciclib or fulvestrant, or loperamide hydrochloride, or drugs with similar chemical structures

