These assumed PFS rates and the expected PFS rates are based on the current knowledge and expectations regarding xentuzumab and its combination partners. The assumed true PFS rate for each cohort is considered clinically relevant. All calculations were performed using R version 3.2.2.

Cohort F:

In expansion cohort F, 20 patients will be treated at the MTD/RP2D.

Assuming a true DC rate of 60%, a sample size of 20 patients leads to a probability of 87% of observing at least 10 events. If the true DC rate is higher, i.e. 80%, the probability of observing at least 10 events is higher than 99%. The probability to observe a false positive signal, i.e. to observe at least 8 events if the underlying true DC rate is 20%, is only 3%. [Table 7.7: 4](#) summarizes the probabilities of observing certain DC rates based on different assumptions on underlying DC rates.

Table 7.7: 4

Disease Control rates for Cohort F

True DC rate	Patients	Probability to observe at least									
		7 events	8 events	9 events	10 events	11 events	12 events	13 events	14 events	15 events	
60%	20	0.99	0.97	0.94	0.87	0.76	0.60	0.42	0.25	0.13	
80%	20	>0.99	>0.99	>0.99	>0.99	>0.99	0.99	0.97	0.91	0.80	
20%	20	0.09	0.03	< 0.01	< 0.01	< 0.01	< 0.01	< 0.01	< 0.01	< 0.01	

A DC rate of 60% would be considered clinically relevant in HR+, Her2- locally advanced and/or metastatic breast cancer patients after prior therapy with a different CDK4/6 inhibitor and aromatase inhibitor (cohort F).

These assumed and expected DC rates are according to the current knowledge and expectations regarding xentuzumab and its combination partners. The calculations were performed using R version 3.2.2.

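### Cohort F's criterion 13 requires resistance to AI and CDK4/6 inhibitor therapy but defines it by progression on either, so its disease-control rate need not describe CDK4/6-resistant disease

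*Protocol*

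**What the plan says.** The opening clause of criterion 13 admits "Patients with resistance to prior therapy with an aromatase inhibitor (AI) and CDK4/6 inhibitor (excluding abemaciclib) for locally advanced or metastatic breast cancer". The clause that follows says what counts as resistance: "defined as radiologic evidence of disease progression while on, or within 30 days after last dose of AI and/or CDK4/6 inhibitor (excl. abemaciclib"), with the drug or drugs given as first-line treatment. The first clause joins the two drugs with *and*, the second with *and/or*. The criterion ends with a limit on earlier treatment: "Patients may not have received more than 1 line of prior endocrine based therapy or any prior chemotherapy for advanced/metastatic disease".

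The population is described elsewhere as follows:

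- Protocol 2.2 (objective): patients "who have progressed following prior therapy with an aromatase inhibitor and a different CDK4/6 inhibitor (excluding abemaciclib").
- Protocol synopsis: patients "who have progressed following endocrine therapy (aromatase inhibitor) and prior CDK inhibitor treatment".
- Protocol 7.7: a DC rate of 60% would be clinically relevant "after prior therapy with a different CDK4/6 inhibitor and aromatase inhibitor (cohort F").

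On size, 7.7 states "In expansion cohort F, 20 patients will be treated at the MTD/RP2D". It gives an 87% chance of at least 10 events if the true DC rate is 60%, and a 3% chance of at least 8 events, called a false positive signal, if it is 20%. SAP 7.4.4 plans one count and one percentage for cohort F. The SAP text that is available plans no split by the drug on which the patient progressed.

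**The concern.** The opening clause and the definition admit different patients. Take a patient who starts an AI with palbociclib or ribociclib, stops the CDK4/6 inhibitor after a few weeks for toxicity, stays on the AI and progresses months later. She has had both drugs and has progressed on the AI, so the *and/or* definition is met. She has no documented progression on, or close to, a CDK4/6 inhibitor.

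This matters for what the primary result of cohort F can be said to show. The regimen contains abemaciclib, itself a CDK4/6 inhibitor, and fulvestrant. Protocol 1.2 reports that this pair lengthened progression-free survival over fulvestrant alone in a randomised trial (median 16.4 against 9.3 months). A patient whose disease has not escaped CDK4/6 inhibition might stay controlled for 24 weeks on that backbone. With no control arm and one pooled percentage, such patients could lift the DC rate without any activity in resistant disease.

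**Working it through.** **1. Does another criterion close the gap?**

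- Exclusion 7 (Protocol 3.3.3) bars palbociclib or ribociclib in the 14 days before trial treatment. That is a minimum interval; there is no maximum.
- Exclusion 8 bars prior abemaciclib in cohort F. It does not require progression on another CDK4/6 inhibitor.
- The one-line limit puts the AI and the CDK4/6 inhibitor in the same line for advanced disease, but drugs started together can stop at different times.

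None of the three excludes the patient described above.

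**2. The protocol's own figures.** With X ~ Binomial(20, p):

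- P(X ≥ 10 | p = 0.60) = 0.8725 (stated: 87%)
- P(X ≥ 8 | p = 0.20) = 0.0321 (stated: 3%)

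Both reproduce.

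**3. A mixed cohort.** Let k of the 20 patients not have progressed on the CDK4/6 inhibitor and have DC rate s. The other 20 − k have 20%. Then

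P(≥ 8) = Σ (i = 0 to k) P(Bin(k, s) = i) × P(Bin(20 − k, 0.20) ≥ 8 − i)

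and the expected DC rate is [k·s + (20 − k)·0.20] / 20.

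The documents give neither k nor s. Applying 20% to resistant patients is also an assumption. All three are illustrative.

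Example with k = 2 and s = 0.40: 0.36 × 0.0163 + 0.48 × 0.0513 + 0.16 × 0.1329 ≈ 0.052. The expected rate is (2 × 0.40 + 18 × 0.20) / 20 = 22%.

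| DC rate s in patients not progressed on the CDK4/6 inhibitor | k = 2 | k = 4 | k = 5 |
|---|---|---|---|
| 20% (no difference): P(≥ 8) | 0.032 | 0.032 | 0.032 |
| 40%: P(≥ 8) | 0.052 | 0.080 | 0.097 |
| 40%: expected DC rate | 22% | 24% | 25% |
| 60%: P(≥ 8) | 0.075 | 0.154 | 0.210 |
| 60%: expected DC rate | 24% | 28% | 30% |

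**The case against.** The strongest reply has four parts.

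*The stated objective is looser than resistance to both drugs.* Section 2.2 and the synopsis speak of progression following this prior therapy, and 7.7 of patients after it. Someone who had both drugs and then progressed on the AI fits those words. This stands, and it is why narrowing the entry criterion is a debatable design choice. It does not remove the conflict inside criterion 13, and it does not make the pooled rate a measure of activity in CDK4/6-resistant disease.

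*Any bias is hypothetical.* Stopping a CDK4/6 inhibitor without progression does not show that the tumour is still sensitive. If these patients do no better, nothing changes. The 20% in 7.7 is not tied to resistant disease either; the same 20/60/80% grid serves objective response in cohort E. All of this stands, so the effect is stated as conditional.

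*The trial is descriptive.* Section 7.2 plans no formal test, and 8 events is an illustration rather than a decision rule. No error rate is broken. The 3% is still the protocol's own account of how often a false signal would appear.

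*Changing entry now may have little effect.* The current protocol recommends stopping xentuzumab and is moving towards termination. This stands for the entry rule but not for the analysis.

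A reader might also infer that a patient with no CDK4/6 inhibitor exposure, treated first-line with an AI alone, meets the *and/or* definition and so fits both cohort F and cohort D2. The documents do not support this. The opening clause of criterion 13, the objective, the synopsis and 7.7 all presuppose prior CDK4/6 inhibitor treatment, while exclusion 8 says "For cohorts D1 and D2 only: prior treatment with palbociclib or ribociclib is also excluded", and abemaciclib is barred in all three cohorts. For the same reason D2's reference rate of 52% progression-free at 18 months should not be used to size the effect: it belongs to patients who cannot enter cohort F.

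**Conclusion.** The point holds as an internal contradiction with a limited consequence. Criterion 13 admits patients who received a CDK4/6 inhibitor, stopped it without progressing, and progressed later on the AI alone. As planned, the cohort F DC rate mixes them with patients who progressed on the CDK4/6 inhibitor.

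If they do better, the rate is inflated as evidence in resistant disease. With 2 to 5 such patients among 20 and a DC rate of 40% to 60%, the chance of at least 8 events moves from 3% to between 5% and 21%. If their rate is also 20%, it stays at 3%. This range rests on an assumed share, an assumed rate, and 20% taken as the rate in resistant disease. It does not show that the rate will be inflated. The 87% and 3% in 7.7 are computed correctly. This is a worthwhile, low-cost improvement to the interpretation of cohort F, not a fault that invalidates the cohort.

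**What to change.** 1. Reconcile the two halves of criterion 13, stating whether progression on the CDK4/6 inhibitor itself was required or only prior exposure to it. Even if few or no further patients enter, this settles whom the cohort describes.
2. In SAP 7.4.4, add the cohort F DC count and percentage for patients with radiologic progression on, or within 30 days after the last dose of, the CDK4/6 inhibitor, beside the all-treated figures. Base any statement about CDK4/6-resistant disease on that subset.

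The data are already planned: Protocol 5.6 collects start and end dates of earlier anticancer treatments and the reason each was stopped. The cost is a one-line clarification and one extra table. The subset has a smaller denominator, so its rate is less precise. Because 5.6 accepts dates given as month and year only, some patients near the 30-day limit will need a check against source records.

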3.3.3 Exclusion criteria

Cohorts A, B, C, D (dose finding), and E:

1. Any documented active or suspected malignancy or history of malignancy, other than the disease under study, within 3 years prior to screening, except appropriately treated basal cell carcinoma of the skin or *in situ* carcinoma of uterine cervix or ductal carcinoma *in situ* (DCIS) if properly treated in opinion of the investigator.
2. Patients who must or wish to continue the intake of restricted medications (see [Section 4.2.2.1](#)) or any drug considered likely to interfere with the safe conduct of the trial
3. Previous treatment in this trial

Proprietary confidential information © 2024 Boehringer Ingelheim International GmbH or one or more of its affiliated companies

4. Currently enrolled in another investigational device or drug study, or less than 21 days since ending another investigational device or drug study(s), or receiving other investigational treatment(s).
5. Chronic alcohol or drug abuse or any condition that, in the investigator's opinion, makes them an unreliable study subject or unlikely to complete the trial
6. Women who are pregnant, nursing, or who plan to become pregnant while in the trial. Men who plan to father a child while in the trial.
7. Prior anti-cancer chemotherapy, biological or radiation therapy, androgens, thalidomide, other anticancer agents, or any investigational drug within 21 days (14 days for non-myelosuppressive agents); and/or 4 weeks for immunotherapy, before starting any of the trial drugs.
8. Prior anti CDK agents
9. Prior radiotherapy to $\geq 25\%$ of bone marrow regardless of when it was received
10. Unresolved treatment related toxicity from previous therapy of $>$ CTCAE grade 1 at study entry (except for stable sensory neuropathy \leq CTCAE grade 2 and alopecia)
11. Previous treatment with IGF-1R targeting compounds
12. Known active uncontrolled or symptomatic CNS metastases, carcinomatous meningitis, or leptomeningeal disease, as indicated by clinical symptoms, cerebral oedema, and/or progressive growth. History of CNS metastases or cord compression are eligible if they have been definitively treated (e.g. radiotherapy, stereotactic surgery) and are clinically stable, off anticonvulsants and steroids for at least 4 weeks. Patients with brain metastases are eligible if they are asymptomatic, completed radiotherapy for at least 4 weeks or are on a stable dose of steroids for at least 4 weeks. Patients are not eligible if they have spinal cord compression.
13. The patient has serious and/or uncontrolled pre-existing medical condition(s) that, in the judgement of the Investigator, would preclude participation in this study, including interstitial lung disease, severe dyspnoea at rest or requiring oxygen therapy.
14. Inadequate bone marrow reserve or organ function as demonstrated by any of the following: ANC $< 1.5 \times 10^9/L$, platelets $< 100 \times 10^9/L$, haemoglobin $< 90g/L$, ALT $> 2.5 \times ULN$ or $> 5 \times ULN$ in the presence of liver metastases, total bilirubin $> 1.5 \times ULN$ or $> 3 \times ULN$ in patients with Gilbert's Syndrome, serum creatinine $> 1.5 \times ULN$ concurrent with creatinine clearance $\leq 50 \text{ mL/min}$.
15. Pre-existing renal disease including glomerulonephritis, nephritic syndrome, Fanconi Syndrome or renal tubular acidosis
16. Refractory nausea and vomiting, chronic GI diseases, inability to swallow the product, or previous significant bowel resection that would preclude adequate absorption of abemaciclib or resulting in baseline Grade 2 or higher diarrhoea.
17. History of hypersensitivity to active or inactive excipients of xentuzumab, abemaciclib or letrozole/anastrozole/fulvestrant, or loperamide hydrochloride, or drugs with similar chemical structures
18. Patients with Diabetes Type I or uncontrolled Type II (defined by HgBA1C $> 8\%$).
19. Patients with advanced/metastatic, symptomatic, visceral spread, that are at risk of life-threatening complications in the short term including patients with massive uncontrolled effusions (pleural, pericardial, peritoneal), pulmonary lymphangitis, and over 50% of liver involvement in metastases.
20. Prior hematopoietic stem cell or bone marrow transplant

21. Have a personal history of any of the following conditions: syncope of cardiovascular etiology, ventricular arrhythmia (including but not limited to ventricular tachycardia and ventricular fibrillation), or sudden cardiac arrest. Subjects with controlled atrial fibrillation for >30 days prior to study treatment are eligible.
22. Erythropoietin, G-CSF, and GM-CSF are not allowed within 2 weeks prior to study. The primary prophylactic use of G-CSF is not permitted but it may be used to treat treatment-emergent neutropenia.
23. Have had major surgery (excluding biopsy) < 28 days of the initial dose of any of the study drugs or planned major surgery during study participation.
24. Have active bacterial or fungal infection (that is, requiring IV antibiotics or therapy at time of initiating study treatment), and/or known viral infection (for example, human immunodeficiency virus [HIV] antibodies, hepatitis B surface antigen, or hepatitis C antibodies). Screening is not required for enrolment.
25. Patients with baseline Grade ≥ 2 hyperglycaemia or patients with baseline Grade ≥ 2 diarrhoea
26. Patients needing treatment with CYP3A4 inhibitors/inducers cannot be included in the trial. (See [Appendix 10.1](#))

Cohort D1, Cohort D2 and Cohort F (Breast Cancer):

1. Any documented active or suspected malignancy or history of malignancy (including inflammatory breast cancer), other than the disease under study, within 3 years prior to screening, except appropriately treated basal cell carcinoma of the skin or *in situ* carcinoma of uterine cervix or ductal carcinoma *in situ* (DCIS) if properly treated in opinion of the investigator.
2. Patients who must or wish to continue the intake of restricted medications (see [Section 4.2.2.1](#)) or any drug considered likely to interfere with the safe conduct of the trial
3. Previous treatment in this trial
4. Currently enrolled in another investigational device or drug study, or less than 21 days since ending another investigational device or drug study(s), or receiving other investigational treatment(s).
5. Chronic alcohol or drug abuse or any condition that, in the investigator's opinion, makes them an unreliable study subject or unlikely to complete the trial
6. Women who are pregnant, nursing, or who plan to become pregnant while in the trial.
7. Prior anti-cancer chemotherapy, biological or radiation therapy, androgens, thalidomide, other anticancer agents, or any investigational drug within 21 days (14 days for non-myelosuppressive agents); and/or 4 weeks for immunotherapy, before starting any of the trial drugs. For cohort F only: prior palbociclib or ribociclib treatment within 14 days before starting any of the trial drugs.
8. Have received prior treatment with chemotherapy (except for neoadjuvant/adjuvant chemotherapy), fulvestrant, everolimus, alpelisib or abemaciclib. For cohorts D1 and D2 only: prior treatment with palbociclib or ribociclib is also excluded
9. Prior radiotherapy to $\geq 25\%$ of bone marrow regardless of when it was received
10. Unresolved treatment related toxicity from previous therapy of > CTCAE grade 1 at study entry (except for stable sensory neuropathy \leq CTCAE grade 2 and alopecia)
11. Previous treatment with IGF-1R targeting compounds
12. Have clinical evidence or history of central nervous system metastasis. Screening is not required for enrolment.

Proprietary confidential information © 2024 Boehringer Ingelheim International GmbH or one or more of its affiliated companies

13. The patient has serious and/or uncontrolled pre-existing medical condition(s) that, in the judgement of the Investigator, would preclude participation in this study, including interstitial lung disease, severe dyspnoea at rest or requiring oxygen therapy.
14. Inadequate bone marrow reserve or organ function as demonstrated by any of the following: ANC $< 1.5 \times 10^9/L$, platelets $< 100 \times 10^9/L$, haemoglobin $< 90g/L$, ALT $> 2.5 \times ULN$ or $> 5 \times ULN$ in the presence of liver metastases, total bilirubin $> 1.5 \times ULN$ or $> 3 \times ULN$ in patients with Gilbert's Syndrome, serum creatinine $> 1.5 \times ULN$ concurrent with creatinine clearance $\leq 50 \text{ mL/min}$.
15. Pre-existing renal disease including glomerulonephritis, nephritic syndrome, Fanconi Syndrome or renal tubular acidosis
16. Refractory nausea and vomiting, chronic GI diseases, inability to swallow the product, or previous significant bowel resection that would preclude adequate absorption of abemaciclib or resulting in baseline Grade 2 or higher diarrhoea.
17. History of hypersensitivity to active or inactive excipients of xentuzumab, abemaciclib or fulvestrant, or loperamide hydrochloride, or drugs with similar chemical structures
18. Patients with Diabetes Type I or uncontrolled Type II (defined by HgBA1C $> 8\%$).
19. Patients with advanced/metastatic, symptomatic, visceral spread, that are at risk of life-threatening complications in the short term including patients with massive uncontrolled effusions (pleural, pericardial, peritoneal), pulmonary lymphangitis, and over 50% of liver involvement in metastases.
20. Prior hematopoietic stem cell or bone marrow transplant
21. Have a personal history of any of the following conditions: syncope of cardiovascular etiology, ventricular arrhythmia (including but not limited to ventricular tachycardia and ventricular fibrillation), or sudden cardiac arrest. Subjects with controlled atrial fibrillation for > 30 days prior to study treatment are eligible.
22. Erythropoietin, G-CSF, and GM-CSF are not allowed within 2 weeks prior to study. The primary prophylactic use of G-CSF is not permitted but it may be used to treat treatment-emergent neutropenia.
23. Have had major surgery (excluding biopsy) < 28 days of the initial dose of any of the study drugs or planned major surgery during study participation.
24. Have active bacterial or fungal infection (that is, requiring IV antibiotics or therapy at time of initiating study treatment), and/or known viral infection (for example, human immunodeficiency virus [HIV] antibodies, hepatitis B surface antigen, or hepatitis C antibodies). Screening is not required for enrolment.
25. Patients with baseline Grade ≥ 2 hyperglycaemia or patients with baseline Grade ≥ 2 diarrhoea
26. Patients needing treatment with CYP3A4 inhibitors/inducers cannot be included in the trial. (See [Appendix 10.1](#))
27. Have initiated bisphosphonates or approved RANK ligand (RANK-L) targeted agents (for example, denosumab) < 7 days prior to initiation of any study drug.

